## **Study Objectives**

The objective of this project is to define the effectiveness and therefore the role of NIR vein finders in adult patients with difficult peripheral venous access. The specific objective of the proposed randomized controlled trial is to test the clinical success rate of placing peripheral venous catheters in 'difficult' access patients using traditional peripheral venous catheter placement compared to two established methods utilizing NIR vein imaging. We hypothesize that the capability to successfully place lasting peripheral venous catheters is increased with the adjunct of the imaging technology, reducing the number of failed needle sticks, reducing the number of peripheral venous catheters placed throughout a patient's hospital stay, and reducing the need for more invasive catheters such as PICC lines. To test this hypothesis, we utilize a commercially available FDA-approved NIR vein finder which currently is already in clinical use at Lahey Hospital & Medical Center. We are planning to conduct a randomized controlled trial recruiting patients who as part of their routine clinical care will require placement of a peripheral venous catheter and who are considered to have a difficult peripheral venous access. Potential study patients will be randomized into 3 groups:

- Placement of peripheral venous catheter using conventional methods
- Use of a VeinViewer to visualize the most suitable target. Once the target has been identified and marked, the device will be placed aside and the peripheral venous catheter will be placed using conventional methods
- Identification of the most suitable target and placement of a peripheral venous catheter under constant imaging with a VeinViewer

To achieve the goals of this project, we have assembled a highly interdisciplinary team with expertise in clinical peripheral venous catheter placement, biomedical device development, and biostatistics to pursue the following specific aims:

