### **Secondary Objectives**

- to compare variables representing the ease of peripheral venous catheter placement, complication rates, and durability of the catheter within each study treatment arm

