### **Follow-Up (for in-patients only)**

A member of the Vascular Access Team will see the patient in person three days after peripheral venous cannulation and each day thereafter according to routine practice. At the follow-up evaluation patency of the peripheral venous catheter and any complications associated with the peripheral venous catheter will be clinically assessed and documented. Follow-up will be completed once the patient has been discharged from the hospital or once the peripheral venous catheter placed as part of the study has been removed or replaced.

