### **Data Collection**

*The following variables will be assessed for all study patients at the time of peripheral venous cannulation:*

a) primary outcome measures:

- rate of successful initial placement of a peripheral venous catheter (investigators have up to 30 minutes or ONE attempt before the study allows for change of technique to the preference of the Vascular Access Team member)

b) secondary outcome measures:

- number of required needle sticks before successful placement of a peripheral venous catheter
- type of method that resulted in successful placement of a peripheral venous catheter
- number of visible veins suitable for cannulation (each continuous vein will be counted as one cannulation site)
- IV catheter gauge size utilized after completion of IV cannulation
- target vein location (bend of the elbow, forearm, back of hand, other) and side of extremity (right vs. left)
- use of warming of arm
- procedure time
- procedure associated complications
- Vascular Access Team member experience (years in practice)
- Vascular Access Team member survey:
  - subjective difficulty locating a suitable vein
  - subjective difficulty of venous access
  - subjective reasons for the difficulty of identifying veins
  - subjective impression of locating additional veins with VeinViewer device
  - subjective impression of usefulness of the VeinViewer device in successful placement of a peripheral venous catheter
- Patient survey:
  - usual number of IV attempts required
  - patients' satisfaction after completion of IV cannulation

c) clinical patient demographics will be derived from patient history and/or medical records:

- age
- gender
- height

- weight
- dominant hand
- date of procedure

*The following variables will be assessed for all in-patient study subjects, if available, at the time of follow-up:*

- catheter patency / need for replacement of catheter / type of catheter used for replacement
- presence of complications such as :
  - hematoma
  - phlebitis
  - thrombophlebitis
  - infiltration
  - nerve damage

All abstracted data, including a study number for each patient, will be stored on a password-protected research database on a hospital server at Lahey Hospital & Medical Center. Any identifier, except for date of procedure, will be removed after the follow-up has been completed.

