## **Study Monitoring and Safety Plan**

### **Study Monitoring**

After the first patient has been enrolled, the principle investigator will review the collected data every four weeks with other members of the study staff. At each research meeting, the principle investigator will evaluate study progress and assess protocol compliance. This will include the informed consent procedure, compliance with eligibility criteria, and identification of protocol violations. The principle investigator will also review all collected data to verify data accuracy, consistency, and integrity. The patients will be physically evaluated 3 days after the procedure by a Vascular Access Team member according to routine practice, unless discharged home or otherwise not available in-hospital, to assess for procedure related adverse events. The principle investigator will review any reports that could be pertinent to a potential adverse event. The principle investigator will be responsible for reviewing data from any adverse event and determining, if applicable, whether the research should be altered or stopped. Any decision to alter or stop enrollment will be reported to the IRB.

Any untoward medical event considered related or possibly related to study participation will be considered an adverse event. Serious adverse events (SAE) will be defined as stated in the IRB SAE reporting policy. Adverse events will be graded for severity according to NCI-CTCAE (version 4.0). For the purpose of safety reporting, the study period will be considered from the day of the procedure to the day of the last follow-up. All adverse events of grade II or greater attributable to study participation will be reported to the IRB. Multiple occurrences of an adverse event that, based on an aggregate analysis, is determined to be an unanticipated problem independent of the severity grade will be reported to the IRB. Any SAEs related to study participation will be reported within 5 business days of the PI learning of the event.

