### **Importance of the Knowledge To Be Gained**

Currently, finding a suitable peripheral vein for access continues to be a frequent challenge for healthcare providers and a significant burden to the patient; issues that are hoped to be addressed by the study device. Due to the sheer volume of peripheral venous catheter placements within the in-hospital setting and the associated detriments to the patient when repeated attempts are needed, any improvement in reducing the number of attempts of peripheral vein cannulations, prolonging the patency of these catheters, and reducing catheter associated complications can have a significant impact on overall patient care throughout the entire in-hospital patient population.

The proposed clinical trial will establish the potential of incorporating a novel NIR vein finder into clinical practice to improve peripheral venous access for in-hospital patients who are considered a 'difficult stick'. Incorporation of such devices, if found to be successful, can fundamentally change patients' experience and reduce complication rates.

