## **Limitations**

Overall it is felt that the study has a very robust design. Yet, limitations include bias by any Vascular Access Team member who may favor one method and therefore might create more favorable results with the method of subjective preference (observer-expectancy effect and experimenter bias).

The follow-up was felt to be adequate since most complications are expected to present during the hospital stay. However, long-term complications, such as thrombophlebitis, might be slightly underestimated due to its sometimes later presentation even after removal of the catheter or in patients who have been transferred to a different facility with the catheter still in place. Nevertheless, there is currently no reason to believe that long-term outcomes of a successful peripheral venous catheter are dependent on the method of catheter placement and therefore it is not expected that the study results will significantly be affected.

NIR vein imaging might require a learning curve. To minimize the issue, all Vascular Access Team members have been trained with the device and had to use the device independently during routine patient care for at least 20 cases before being able to participate in the study.

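### Catheter durability is a secondary objective, but no date, time or reason of study-catheter removal is listed for collection, so time to catheter failure cannot be compared between arms

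*Combined protocol and SAP*

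**What the plan says.** Secondary Objectives includes a comparison of "complication rates, and durability of the catheter within each study treatment arm". Study Objectives states the hypothesis that "the capability to successfully place lasting peripheral venous catheters is increased with the adjunct of the imaging technology". Importance of the Knowledge To Be Gained lists "prolonging the patency of these catheters" among the improvements sought.

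Under Follow-Up (for in-patients only), a Vascular Access Team member "will see the patient in person three days after peripheral venous cannulation and each day thereafter according to routine practice". Follow-up is complete at discharge or "once the peripheral venous catheter placed as part of the study has been removed or replaced". Study Monitoring adds that the day-3 evaluation takes place "unless discharged home or otherwise not available in-hospital".

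For the follow-up visit, Data Collection lists "catheter patency / need for replacement of catheter / type of catheter used for replacement" and the presence of complications, for in-patients and only if available. The one date on its list is the date of the procedure. Data Analysis and Statistical Methods promises routine tests for primary and secondary outcomes. It gives no durability measure and no rule for catheters that come out for reasons other than failure.

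**The concern.** Durability rests on two facts: when the catheter came out and why. The plan makes removal one of the events that closes follow-up, yet asks nobody to write down when it happened or for what reason. If the plan is followed exactly, a named secondary objective and the word 'lasting' in the hypothesis can be answered only as status at a check. A catheter taken out because it was no longer needed may look the same in the data as one that failed and was not replaced. Catheters lost before day 3 would be the least well described.

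**Working it through.** **The plan's own figure.** The only sample-size figure is 125 per group, for the primary endpoint (Sample Size and Power Determination: 50% against 70% success, 80% power, two-sided 0.0167). The pooled-variance formula without continuity correction is

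n = [z(α/2)·√(2·p̄·(1−p̄)) + z(β)·√(p1(1−p1)+p2(1−p2))]² / (p1−p2)²

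With p̄ = 0.60, z(α/2) = 2.393 and z(β) = 0.842, this is [2.393·√0.48 + 0.842·√0.46]² / 0.04 = (1.658 + 0.571)² / 0.04 ≈ 124.2, rounded up to 125. Power at 125 per group is 80.3%. The figure reproduces and does not involve durability. The rest of the check is a comparison of sections.

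**What a durability analysis needs against what is listed.**

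| Needed | Listed in Data Collection? |
|---|---|
| Start of dwell | Date of procedure: yes |
| Date and time of removal | No |
| Reason for removal | No; need for replacement and complications are indirect clues |
| Date of discharge with the catheter in place | No |
| Status at a check | Yes: patency, need for replacement, type of replacement |
| Method that placed the catheter | Yes, at the time of cannulation |

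**What the visit schedule can recover.** Visit dates are not listed either, but suppose they are kept. A catheter found out at the first check came out somewhere between day 0 and day 3, a window of 3 × 24 = 72 hours. At later daily checks the window is about 24 hours. A patient discharged before day 3 has no scheduled check.

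**Four in-patients under the listed variables.**
1. The catheter is removed on day 1 because it is no longer needed. The day-3 record shows no need for replacement and no complication.
2. The catheter comes out accidentally on day 1 and no further access is needed. The record can be the same as in case 1, although this is a failure.
3. The catheter infiltrates on day 1 and is replaced. Need for replacement, replacement type and the complication can all be recorded, so the failure is identified, but its time is known only to within 72 hours.
4. The catheter is working when the patient is discharged on day 2. There is no check and no listed date at which to censor.

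The listed items identify case 3 as a failure, cannot separate cases 1 and 2, and leave case 4 without an end date.

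**Which method placed the catheter.** Peripheral Venous Cannulation and Randomization of Study Groups allows a change of technique after one attempt or 30 minutes. At the planning rates, initial placement fails in 1 − 0.50 = 50% of control patients and 1 − 0.70 = 30% of patients in an imaging arm. If all of those then received a catheter by another technique, 50% and 30% of study catheters would have been placed by a non-assigned method. These are upper limits at the planning rates, because some patients may stay with the assigned technique or end with no catheter. A by-arm durability comparison would be diluted to that extent even with perfect removal dates.

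**The case against.** The best defence is that durability is never defined as time to failure. Patency and replacement status, checked on day 3 and daily after that, support a comparison between arms, and the complication list helps to identify failures. This stands in part. A reader might infer that durability is not measured at all, and the documents do not support that. What is missing is timing and a clean separation of failure from elective removal.

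Study Monitoring also runs the safety period to the day of the last follow-up, so that day must be known to the team. This narrows the gap without closing it. The day is a boundary for safety reporting, is not a listed data item, and says nothing about reason.

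Limitations defends the follow-up on the ground that there is "no reason to believe that long-term outcomes of a successful peripheral venous catheter are dependent on the method of catheter placement". That remark concerns complications that appear late. It sits uneasily with the hypothesis of more lasting catheters, but it is not a flat contradiction, and an assumption of no difference cannot stand in for data on a stated comparison.

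A reader might also infer that the trial fails to collect two of its endpoints, because the hypothesis in Study Objectives mentions fewer peripheral catheters over the stay and less need for PICC lines. Neither is a named objective or endpoint. Both are captured up to the first replacement, and a PICC that directly replaces the study catheter would be recorded. This is a mismatch of wording.

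**Conclusion.** The point holds and should be corrected. As written, the plan yields patency or replacement status at checks from day 3, for in-patients where available. It does not yield dwell time or time to catheter failure, and it separates failure from elective removal only in part. The conclusion rests on the listed variables being the full set. If the case report form already holds removal date and reason, only the protocol text needs changing.

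The documents allow the uncertainty in removal time to be stated (about 72 hours at the first check, about 24 hours later, and only if visit dates are kept). They give no failure rate, replacement rate, length of stay or in-patient share, so no figure can be put on bias or lost power for durability. A reader might infer that the trial's main conclusion is at risk. It is not: the primary endpoint is assessed at cannulation, and its sample size reproduces.

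**What to change.** - **Data Collection:** for every randomised in-patient with a study catheter, add the date, time and reason of its removal, or the date of discharge with the catheter in place.
- **Data Analysis and Statistical Methods:** compare durability by randomised group as time from insertion to catheter failure, with elective removal and discharge treated as censoring or competing events. Report the number without a catheter in each arm, because those patients drop out of the comparison after randomisation.
- **Supplement:** since technique is free after one attempt or 30 minutes, also report durability by the method that succeeded, which is already recorded. Label this descriptive and non-randomised.
- **Study Objectives (wording only):** narrow the hypothesis on catheters per stay and PICC use to the need for, and type of, a first replacement.

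The cost is a few data fields and a little more analysis. There are no extra visits or patients and no change to the primary analysis. The wording change gives up the per-stay question, which the named endpoints do not ask.

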### **Data Collection**

*The following variables will be assessed for all study patients at the time of peripheral venous cannulation:*

a) primary outcome measures:

- rate of successful initial placement of a peripheral venous catheter (investigators have up to 30 minutes or ONE attempt before the study allows for change of technique to the preference of the Vascular Access Team member)

b) secondary outcome measures:

- number of required needle sticks before successful placement of a peripheral venous catheter
- type of method that resulted in successful placement of a peripheral venous catheter
- number of visible veins suitable for cannulation (each continuous vein will be counted as one cannulation site)
- IV catheter gauge size utilized after completion of IV cannulation
- target vein location (bend of the elbow, forearm, back of hand, other) and side of extremity (right vs. left)
- use of warming of arm
- procedure time
- procedure associated complications
- Vascular Access Team member experience (years in practice)
- Vascular Access Team member survey:
  - subjective difficulty locating a suitable vein
  - subjective difficulty of venous access
  - subjective reasons for the difficulty of identifying veins
  - subjective impression of locating additional veins with VeinViewer device
  - subjective impression of usefulness of the VeinViewer device in successful placement of a peripheral venous catheter
- Patient survey:
  - usual number of IV attempts required
  - patients' satisfaction after completion of IV cannulation

c) clinical patient demographics will be derived from patient history and/or medical records:

- age
- gender
- height

- weight
- dominant hand
- date of procedure

*The following variables will be assessed for all in-patient study subjects, if available, at the time of follow-up:*

- catheter patency / need for replacement of catheter / type of catheter used for replacement
- presence of complications such as :
  - hematoma
  - phlebitis
  - thrombophlebitis
  - infiltration
  - nerve damage

All abstracted data, including a study number for each patient, will be stored on a password-protected research database on a hospital server at Lahey Hospital & Medical Center. Any identifier, except for date of procedure, will be removed after the follow-up has been completed.

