In the clinical setting, NIR technology has shown to significantly increase the number of identifiable possible cannulation sites compared with normal eyesight [3,4]. However, the improvement in visualization did not automatically translate into improvement in successful cannulation of veins. Specifically, the efficacy of these vein finding devices has shown limited benefit when tested in the pediatric in-hospital population with a nonselective use in all patients. A meta-analysis of 11 RCTs concluded that using NIR light devices did not have an impact on overall failure rate at the first attempt at peripheral intravenous cannulation (PIVC) in pediatric patients [5]. Similarly, in studies evaluating the number of attempts required for successful PIVC found no difference between the NIR light device and traditional methods [6]. Many investigators subjectively felt the NIR device to be helpful; particularly in selected patients [5]. Yet, subgroup analysis did not define the cohort of pediatric patients that would benefit most from this technology. One publication interpreted these outcomes as such that despite improved visualization of superficial veins, successful venous puncture remains heavily dependent on the skills of the operator [7].

The efficacy of NIR vein finders beyond the first line approach, particularly in patients that have failed conventional peripheral venous access methods or in patients that are expected to be a “difficult stick”, is not established. Conflicting results have been reported in the pediatric literature regarding the subjective benefit of NIR light devices in patients with perceived difficult peripheral intravenous access [6]. In addition, knowledge about the efficacy of these devices in the adult inpatient setting is mostly unknown. The aim of the present study is to address these knowledge gaps.

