### **Eligibility Criteria**

The eligibility criteria were chosen to minimize the risk to the study patient by only including patients who are already planned to undergo placement of a peripheral venous catheter and by excluding any high-risk patients. In order to be considered for the study, patients have to meet the following criteria:

a) Inclusion criteria:

- adult in-hospital patients ( $\geq 18$  years of age, inpatient and outpatient setting)
- willing to provide research authorization
- scheduled and consented to undergo peripheral venous cannulation of one of the upper extremities to be performed by one of the members of the Vascular Access Team
- determined to be a difficult peripheral venous access defined by one of the following criteria in alignment to the A-DIVA scale to be assessed by one of the members of the Vascular Access Team [8]:
  - failed inspection for more than one visible or palpable suitable vein through conventional methods
  - failed at least one attempt of peripheral venous cannulation through any methods
  - history of difficult peripheral venous access
  - greatest diameter of target vein less than 3mm determined by conventional methods

b) Exclusion criteria:

- clinical contraindication for placement of peripheral venous catheter, including:
  - severe bilateral upper extremity edema
  - severe bilateral upper extremity skin burn
  - severe bilateral upper extremity cellulitis
  - history of bilateral axillary lymphadenectomy

- known severe cardiovascular or pulmonary compromise demanding minimization of procedure time, such as:
  - severe shock with severe cardiovascular instability
  - active CPR
  - major uncontrolled hemorrhage
  - any condition for which the primary healthcare provider is requesting emergent venous access
- scheduled PICC or midline catheter placement
- non-English-speaking patients if an interpreter is not available
- prisoner and any individual involuntarily confined or detained in a penal institution
- impaired capacity to make informed medical decisions

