### Peripheral Venous Cannulation and Randomization of Study Groups

Patients, who meet eligibility criteria and agree to participate in the study after an informed consent process, will undergo simple randomization. A sealed envelope holding the information of the random assignment will be opened by the Vascular Access Team member. Randomization will assign study patients into 1 of 3 groups/treatment arms with a 1:1:1 ratio:

- Placement of a peripheral venous catheter using conventional methods
- Use of VeinViewer to visualize the most suitable target. Once the target has been identified and marked, the device will be placed aside and the peripheral venous catheter will be placed using conventional methods
- Identification of the most suitable target and placement of a peripheral venous catheter under constant imaging with VeinViewer

When the VeinViewer device will be utilized, multiple areas on the patient's upper extremities will be assessed looking for the most suitable access point according to routine clinical practice. There is no restriction in regards to vein diameter, vein length, or relation of veins to joints. The choice of the location for intravenous cannulation, the use of tourniquets, the use of heating devices, and any techniques to palpate the vein will be left to the discretion of the Vascular Access Team member based on routine clinical practice. This study requires an unobstructed view of the subject's arm under standard hospital lighting conditions.

Investigators have up to 30 minutes or ONE attempt before the study allows for change of technique to the preference of the Vascular Access Team member.

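### Does the primary outcome need a written score for a patient whose technique changes before any needle stick?

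*Combined protocol and SAP*

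**What the plan says.** Data Collection lists the rate of successful initial placement as the only primary outcome and adds in brackets, on the same line, that "investigators have up to 30 minutes or ONE attempt before the study allows for change of technique". Peripheral Venous Cannulation and Randomization of Study Groups gives the same limit as a procedural rule: "Investigators have up to 30 minutes or ONE attempt before the study allows for change of technique". Neither place says what a change of technique does to the patient's score.

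The primary outcome falls under a heading that covers everyone: "The following variables will be assessed for all study patients at the time of peripheral venous cannulation". Two secondary outcomes record what happens later: "number of required needle sticks before successful placement of a peripheral venous catheter" and "type of method that resulted in successful placement of a peripheral venous catheter". Data Analysis and Statistical Methods plans a direct comparison of the study groups with routine tests and names no analysis set. The groups are the three arms to which patients are randomised 1:1:1. Sample Size and Power Determination assumes 50% success in the control group and 70% in either imaging group.

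**The concern.** The limit has two parts, 30 minutes and one attempt. The time part matters mainly when no stick has been made. The first stick may then be made with a technique the patient was not assigned. If it succeeds, the stick count is the same as for a first-stick success with the assigned technique. An analyst could score this patient in three ways: not a success, excluded, or credited with the later success. Primary Objective and Study Endpoints both tie the rate to the method used rather than to the randomised arm, which could seem to invite the third.

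The case might also be uneven between arms. One entry criterion is "failed inspection for more than one visible or palpable suitable vein through conventional methods", and the conventional arm searches again by those methods. The background section says that "NIR technology has shown to significantly increase the number of identifiable possible cannulation sites compared with normal eyesight". If no-stick cases gathered in the conventional arm, excluding or crediting them would raise that arm's rate and narrow the difference.

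The choice also bears on what the endpoint measures. The background separates seeing a vein from cannulating it: "the improvement in visualization did not automatically translate into improvement in successful cannulation of veins". The score decides whether failure to find a vein with the assigned technique counts in the primary outcome.

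**Working it through.** **1. The plan's own figure.** Inputs from Sample Size and Power Determination: 50% against 70%, two-sided alpha 0.0167, power 80%. The normal quantiles are 2.393 and 0.842, and the pooled rate is 0.60. With pooled variance under the null and no continuity correction:

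n = [2.393·√(2·0.6·0.4) + 0.842·√(0.5·0.5 + 0.7·0.3)]² / 0.20² = 124.2, rounded up to 125 per group.

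This matches the plan. Power by the same formula is 80.3% at 125 per arm and 83.0% at 133 (400/3 ≈ 133).

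**2. What the text implies for a no-stick patient.**
- The limit is part of the primary outcome line, so it bounds what counts as initial placement: the assigned technique, up to the point where a change is allowed. A placement after a change lies outside it.
- The method that eventually worked has its own secondary outcome, so success after a change is recorded there.
- The variables are assessed for all study patients, and the comparison is between the randomised groups.

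Together these give one score: not a success, counted in the assigned arm. The 50% and 70% are then rates on that definition, and step 1 stands unchanged.

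**3. What the other scorings would do.** Let c and r be the no-stick patients in the conventional arm and one imaging arm, 133 each. Successes with the assigned technique are 0.5·133 = 66.5 and 0.7·133 = 93.1.

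- Excluded: 66.5/(133 − c) against 93.1/(133 − r).
- Credited, with success q after the change: (66.5 + qc)/133 against (93.1 + qr)/133, for q = 0.5 or 0.7.

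Example, c = 2 and r = 0, excluded: 66.5/131 = 50.8% against 70.0%, a difference of 19.2 points. Every c, r and q below is assumed.

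| c v r | Excluded: difference, power | q = 0.5 | q = 0.7 |
|---|---|---|---|
| 2 v 2 | 20.3 points, 84.1% | 20.0, 83.3% | 20.0, 83.4% |
| 1 v 0 | 19.6, 81.3% | 19.6, 81.4% | 19.5, 80.8% |
| 2 v 0 | 19.2, 79.3% | 19.3, 79.7% | 18.9, 78.3% |
| 3 v 1 | 19.4, 79.9% | 19.3, 79.9% | 18.9, 78.5% |
| 7 v 2 | 18.3, 73.8% | 18.1, 74.5% | 17.4, 70.5% |

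Equal counts do no harm. From the 1 v 0 and 2 v 0 rows, each extra conventional case takes about 0.4 to 0.5 points off the difference and about 2 points off power. An excess in the imaging arm works the other way: 0 v 2 gives about 86% to 87%.

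**4. How firm the imbalance is.** The inspection criterion is one of four alternatives, any of which is enough for entry. It is met by a patient with exactly one suitable vein, and one vein is enough for a stick. The other three concern a failed earlier attempt, a history of difficult access, and a small target vein, and the last presupposes that a target was found. Palpation, tourniquets and warming are left to the operator. The background reports more identifiable sites, which is not the same as fewer patients with none. An excess in the conventional arm is plausible, but the documents do not establish it.

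**The case for a change.** The strongest case for a change is that this is the primary endpoint of a trial whose operators know the arm, and Limitations concedes that they may favour one method. An unwritten score could be settled after results are seen. Larger imbalances would also be costly. If 10% of conventional patients and no imaging patients had no stick (12.5 of 125 against 0), the difference under the other scorings would be 13 to 15 points and power 40% to 52%. At 5% against 0% it would be 16.5 to 17.5 points and 62% to 68%.

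It stands that the score is not written in words, and that the protocol does not say how the time and attempt parts of the limit combine for a late first stick with the assigned technique. Nor would the method field always reveal a change. Patients in the second arm have the catheter placed conventionally after the vein is marked, so an entry that says only conventional would not separate a change from that arm's own procedure. But initial success is itself listed as a variable to be assessed at the bedside, by staff who know the assignment. It need not be rebuilt from other fields.

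The rest does not stand. The 5% and 10% rates have no source in the documents, and the harm needs a scoring the text does not suggest. Under the imbalance supposed, the alternatives shrink the device's apparent benefit, so they offer no route to a result that flatters it.

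The natural reading does let vein finding contribute. With 60% success per stick in both arms and 10% against 0% no-stick cases, the rates would be 54% and 60%, a 6-point difference from finding alone. That is a proper part of comparing placement strategies, because a patient in whom no vein was found has not had a catheter placed by the assigned technique.

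**Conclusion.** The gap is one of wording that an analyst would fill sensibly from the plan itself: all randomised patients, in the assigned arm, with a change of technique before the first stick counted as not a success. On that reading the planned 20-point difference, the 125 per group and the 80.3% power (83.0% at 133) are unaffected. The conclusion rests on taking the bracketed limit as part of the outcome definition and on comparing the arms as randomised, and the text supports both.

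If an analyst did exclude or credit such patients, one to three conventional cases with at most one imaging case would leave power between about 78% and 81%. Only larger unequal counts would matter, and the documents give no reason to assume a particular count. No change to the plan is called for.
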